6.5.1.2 Suspected Symptomatic VTE

Patients will be evaluated for signs and symptoms of DVT (e.g., swelling, localized pain, redness, heat, localized warmth) and PE (e.g., unexplained shortness of breath, coughing up blood, chest pain that gets worse with a deep breath, unexplained coughing) during the post-surgery in hospital/clinic period and at all visits occurring throughout the Treatment and Follow-up Phases of the study. Patients with suspected DVT and or PE should undergo further diagnostic testing per hospital routine (e.g compression ultrasound for suspected DVT and spiral CT scan for patients with PE). Every suspected episode of DVT or PE must be reported appropriately as an AE and the underlying supportive data (e.g images and reports of diagnostic tests, hospital reports) will be submitted for adjudication by the CIAC. The Study Site Manual for Venography and Event Reporting provides instruction on the documentation, data collection, and reporting required for each suspected episode of DVT or PE.

If patients would have a PE or DVT confirmed by diagnostic testing during the Treatment Phase, the planned venography of the operated leg is not required.

If a patient would have an event that requires therapeutic anticoagulant treatment, the prophylactic dosing of enoxaparin will need to be discontinued. The anticoagulant treatment undertaken will be at the discretion of the treating physician and any question regarding SelK2 should be referred to the medical monitor by contacting the medical help line.

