10.0 STATISTICAL METHODS AND PLANNED ANALYSES

10.1 Sample Size and Power

Assuming that the rate of VTE for the active comparator (enoxaparin) arm of this study will be 25%, it is estimated that a sample size of 76 evaluable patients per arm should give the study 80% power of declaring non-inferiority between the SelK2 arm and the enoxaparin active comparator arm. This calculation uses a one-sided 90% CI with a non-inferiority margin of 15%. This calculation assumes that the underlying rate of VTE for the SelK2 and enoxaparin arms will be identical at 25% and with the non-inferiority margin set as at the midpoint between the expected active therapy response compared to an assumed placebo event rate in this patient population of 55%. Consequently, making the conservative estimate that up to 20% of randomized patients may not yield evaluable endpoint data, a total of 95 patients will be enrolled per arm to provide at least 76 endpoint evaluable patients per arm.

Sample Size Considerations for Adaptive Arm:

With the same assumptions as above the for active comparator (enoxaparin) arm of the study event rate, it is estimated that a sample size of 76 evaluable patients in a combination therapy arm of SelK2 and enoxaparin should give the study 80% power of declaring superiority between the SelK2 and enoxaparin arm and the enoxaparin active comparator arm for an estimated SelK2 and enoxaparin VTE event rate of 6% (an 19% difference between combination treatment effect and active comparator treatment effect). This calculation assumes a two-sided 0.1 alpha, a Pearson Chi-squared test, and a superiority comparison.

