10.2 Analysis Populations

Assignment of patients to analysis populations will be done prior to clinical data lock for the study. The following populations will be defined: Intent-to-Treat (ITT), modified Intent-to-Treat (mITT), Per-Protocol (PP), and Safety.

Intent-to-Treat (ITT): All patients who are randomized. The ITT population will be analyzed by randomized treatment group.

Modified Intent-to-Treat (mITT): All patients in the ITT population who also have a successful venogram or symptomatic VTE event which allow for assessment of the primary efficacy outcome.

Per-Protocol (PP): All mITT patients who complete the study and have no major protocol violations that will impact the efficacy assessments.

Safety: All patients who received at least 1 dose of study drug. Safety population will be analyzed by actual treatment received.

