10.3.3 Efficacy Analyses

For all efficacy analyses, the main analysis will be based on the mITT population. Both primary and secondary endpoint analyses will also be performed on the PP population; these analyses will be supportive only. Comparisons will be made between the SelK2 treated patients SelK2 and enoxaparin treated patients, and the enoxaparin group. The difference of the total VTE rate during the Treatment Phase (from time of randomization up until the day of completion of venogram) between the SelK2, SelK2 and enoxaparin, and enoxaparin treatment groups will be estimated. The lower 1-sided 90% CI of the difference will be calculated and non-inferiority will be concluded if the upper limit of the 90% CI is $\leq 15\%$. The same analysis will be completed on the PP population.

The following secondary analyses will be performed on the mITT and PP populations:

- Comparison of the rates of the individual components of the primary efficacy outcome between the SelK2, SelK2 and enoxaparin, and enoxaparin treatment groups through Treatment Period.
- Conduct primary efficacy analysis of the total VTE rate between the SelK2 treatment, SelK2 and enoxaparin treatment, and enoxaparin treatment with the inclusion of events through Study Day 57.
- Complete comparison of the rates of the individual components of the primary efficacy outcome between the SelK2, SelK2 and enoxaparin, and enoxaparin treatment groups with the inclusion of events through Study Day 57.

Absolute changes from baseline in hsCRP and D-dimer will be summarized by treatment group at each post-baseline visit. Change from baseline in each parameter will be analyzed and compared between treatment groups using a mixed linear model with repeated measures (MMRM).

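### Treatment Phase rates of symptomatic DVT and PE are computed in mITT, which drops followed, event-free patients without a venogram and so biases these rates upward

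*Combined protocol and SAP*

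**What the plan says.** Section 10.3.3 sets the general rule: "For all efficacy analyses, the main analysis will be based on the mITT population". PP is supportive. The component comparisons are planned for the Treatment Phase and again "with the inclusion of events through Study Day 57", and for all of them "The following secondary analyses will be performed on the mITT and PP populations".

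Section 10.2 defines mITT as those ITT patients "who also have a successful venogram or symptomatic VTE event which allow for assessment of the primary efficacy outcome". PP is a subset of mITT that also requires completion of the study. ITT is defined as "All patients who are randomized. The ITT population will be analyzed by randomized treatment group", but no efficacy analysis in Section 10.3.3 uses it.

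Symptomatic events are sought without regard to venography. Section 6.5.1.2 has patients checked for signs and symptoms of DVT and PE "at all visits occurring throughout the Treatment and Follow-up Phases of the study", with every suspected episode sent for blinded adjudication. The same section waives the venogram for a patient whose DVT or PE has been confirmed in the Treatment Phase.

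For planning, Section 10.1 allows that "up to 20% of randomized patients may not yield evaluable endpoint data" and therefore randomises 95 per arm to obtain at least 76 evaluable.

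**The concern.** A denominator restricted to patients with a usable venogram suits asymptomatic DVT, which cannot be seen without one. Symptomatic DVT and PE do not need a venogram. A patient whose venogram failed, but who was followed and had no symptomatic event, has a known negative result for these two components. The mITT rule discards that result. The same patient with an event would have been kept, so membership of the denominator depends on the outcome being counted.

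Symptomatic events are the clinically manifest part of the composite, and readers will set them beside the adjudicated bleeding rates. Section 10.4 reports bleeding in the safety population, so the two would stand on different denominators. The trial is also open-label. If venogram completion differed between arms, the rule would produce a difference in symptomatic rates where none exists.

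**Working it through.** **The plan's own figures.** With both rates at 25%, a margin of 15 points, one-sided alpha 0.10 and 80% power (Section 10.1):

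- n = (1.2816 + 0.8416)² × 2 × 0.25 × 0.75 / 0.15² = 75.1, so 76 per arm. This agrees with the plan.
- 76 / (1 − 0.20) = 95 randomised per arm. This agrees too.

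**Inflation of a Treatment Phase symptomatic rate.** Every patient with a symptomatic DVT or PE is in mITT, so the numerator is the same in ITT and mITT. Only the denominator shrinks. If d is the non-evaluable share, the mITT rate divided by the ITT rate is 1/(1 − d).

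| d | Factor |
|---|---|
| 5% (assumed) | 1.05 |
| 10% (assumed) | 1.11 |
| 15% (assumed) | 1.18 |
| 20% (planning ceiling) | 95/76 = 1.25 |

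In counts, 2 events in an arm are 2/95 = 2.11% of those randomised and 2/76 = 2.63% of mITT. Four events are 4.21% and 5.26%.

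**If 20% is the share without a venogram.** Patients with events then re-enter mITT, and the reported rate is p / (0.80 + 0.20p), where p is the true symptomatic rate (assumed):

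- p = 2%: 0.02/0.804 = 2.49%, a factor of 1.244.
- p = 4%: 0.04/0.808 = 4.95%, a factor of 1.238.

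**Incomplete follow-up.** Suppose half of the 19 non-evaluable patients had no follow-up at all (assumed). The proper comparison is then with 95 − 9.5 = 85.5 patients, and the factor is 85.5/76 = 1.125.

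**Between arms.** Equal d multiplies both rates, and the risk difference, by the same factor. The risk ratio does not change. With 10% versus 20% non-evaluable (assumed) and equal true risk, the spurious ratio is 0.90/0.80 = 1.125. At a true 2% that is 2.22% versus 2.50%, or 0.28 points. The standard error of that difference is √(0.0222 × 0.9778/85.5 + 0.025 × 0.975/76) = 2.4 points.

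**Unexplained death.** Section 3.6.1.1 makes it a component, but the mITT definition does not name it.

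- Read literally, a patient who dies unexplained before venography, with no earlier symptomatic VTE, is outside mITT. The component is under-counted.
- If the adjudicators' attribution of such deaths to PE (Section 6.5.2.1.3) makes the death a symptomatic VTE event, the patient enters mITT and the rate is inflated as above.
- PP requires completion of the study, so it removes patients who die in any case.

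**Through Day 57.** The mITT definition ties entry to assessing the primary outcome, which is a Treatment Phase outcome. Take a late symptomatic event in a patient without a venogram. If it qualifies the patient for mITT, the inflation above applies. If it does not, the patient leaves numerator and denominator alike. There is then no systematic inflation, but a real event is discarded.

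**The case against.** The strongest case against runs as follows. These are secondary analyses and no decision rule uses them. Non-inferiority rests on total VTE. Reporting components on the composite's own set lets the parts reconcile with the whole. Counts will be shown with percentages (Section 10.3.1) and population sizes appear in the disposition table (Section 10.3.2.1), so a reader could largely rebuild the rates. Suspected DVT and PE are also reported as adverse events in the safety population.

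Most of this stands as a limit on importance. It does not remove the defect. The adverse event tables are MedDRA summaries of reported events, not adjudicated component rates by randomised arm, and the component table can be kept on mITT beside an all-randomised one.

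A reader might infer more than the documents support:

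- That all these rates are inflated by a quarter. The 20% is an upper planning figure, which Section 10.1 itself calls conservative.
- That the outcome is known in every randomised patient. All are under surveillance, but Section 8.1 foresees withdrawal, loss to follow-up and withdrawal of consent to further data collection.
- That unexplained death and the Day 57 rates are inflated in the same way. As shown above, this depends on how the mITT definition is read.
- That the arms will be distorted relative to each other. The documents give no differing venogram rates, and in the assumed case the artefact is small beside sampling error.

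**Conclusion.** The concern holds for confirmed symptomatic DVT and PE in the Treatment Phase. The mITT denominator is selected on the outcome and the stated rates are biased upward, by a factor of about 1.25 at the planning ceiling and about 1.05 to 1.18 at 5% to 15% non-evaluable. These factors assume that the dropped patients were followed for symptoms; to the extent that they were not, the inflation is smaller. A spurious risk ratio of about 1.125 needs unequal missingness such as 10% versus 20%, which is an assumption.

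Unexplained death may be under-counted instead, and the Day 57 rates may be inflated or may lose real events. The text has to settle both. Asymptomatic DVT is not affected. The component rates do not enter the non-inferiority rule, so the primary test is untouched by this point. The change is worth making because it is cheap, but it is not critical to the trial's conclusion.

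**What to change.** - **Section 10.3.3, symptomatic components.** Report adjudicated symptomatic DVT, symptomatic PE, unexplained death and the composite of these three in all randomised patients by randomised arm, for the Treatment Phase and through Day 57. Use cumulative incidence with censoring at withdrawal or loss to follow-up. A simple proportion would also do if the number not followed is shown beside it, because it counts those patients as event-free.
- **Section 10.3.3, other endpoints.** Report asymptomatic DVT among patients with an evaluable venogram. Keep mITT for total VTE.
- **Section 10.2.** State in the mITT definition whether an unexplained death qualifies a patient, and in which time window a symptomatic event must fall.

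The cost is a few sentences and one further table, with no new data. The symptomatic rates will be lower, and their denominator will differ from that of the composite, so the components will no longer add up to it. Keeping the mITT component table alongside deals with that.

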10.3.4 Pharmacokinetics and Pharmacodynamics

Serum pre- and post-treatment SelK2 concentrations for evaluable patients receiving SelK2 will be listed by dose, day and patient and also summarized by descriptive statistics.

Potential relationships between selected pharmacodynamics and plasma exposure measures may be explored, where deemed appropriate.

10.4 Safety Analysis

All treatment-emergent AEs and SAEs will be summarized by treatment using the MedDRA coding system, by system organ class, preferred term, relationship to Study Drug and severity (See Section 10.4.1).

Incidence of bleeding events (as adjudicated by the CIAC) including the following will be tabulated by treatment:

- 1) Major Bleeding event (MB),
- 2) Clinically Relevant Non-Major Bleeding event (CRNMB),
- 3) Minor Bleeding event, or
- 4) Combination of MB and CRNMB

Additionally, the overall safety profile of study drug will be assessed in terms of the following safety and tolerability endpoints:

- Incidence of treatment-emergent adverse events (TEAEs),
- Clinical laboratory values (hematology, serum chemistries, urinalysis, and coagulation parameters),
- ECGs,
- Vital signs.

These safety endpoint measures will be tabulated by treatment arm and study visit (and timepoint, where appropriate) and may also be presented as change and percent change from baseline, as appropriate.

Safety analysis will be based on the set of data associated with the period from randomization through the final Follow-Up Phase visit (Day 57). All Safety analyses will be performed on the safety population. Descriptive analysis of the above safety parameters will be performed.

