[REDACTED] Vials are stored refrigerated at 2 to 8°C and protected from light. A pharmacist or designated personnel will compound individual doses of active study drug for patients on a milligram per kilogram basis in a 100 mL infusion bottle or bag of a sterile 0.9% sodium chloride solution (0.9% Sodium Chloride Injection, USP) in accordance with the Pharmacy Manual. Study drug will be administered over 30 minutes by IV infusion.

Active Comparator (Enoxaparin): Commercially available enoxaparin (40 mg in 0.4 mL water

in pre-filled disposable syringes for SC administration) will be provided to the study site pharmacies for use in this study, in accordance with local regulatory requirements. Enoxaparin should be stored in a temperature-controlled environment which is maintained below 25°C; but should not be frozen.

The Pharmacy Manual will provide further details about handling, storage, and mode of administration.

Dose Rationale:

Criteria for Evaluation:

Primary Efficacy Endpoints: The primary efficacy outcome is the composite of asymptomatic deep vein thrombosis (DVT) detected by mandatory unilateral venography of the operated leg or confirmed symptomatic DVT, confirmed symptomatic PE or unexplained death during the Treatment Phase. All efficacy endpoint data will be adjudicated by a blinded Central Independent Adjudication Committee.

Exploratory Efficacy Endpoints: The exploratory efficacy outcomes will include measurements of markers of inflammation and thrombosis (hsCRP and D-dimer, respectively) and other possible PD markers of SelK2 efficacy.

PK, PD, and Immunogenicity Evaluations: Samples will be collected during Treatment and Follow-up Phases for evaluation of PK, PD, and immunogenicity.

Safety:

The primary safety outcome is a composite of major bleeding events or clinically relevant non-major bleeding events during the Treatment Phase. The secondary safety outcomes are the incidence of the composite of major, clinically relevant non-major, or minor bleeding events that occur during the Treatment and Follow-up Phases.

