Other safety evaluations will include assessment of adverse events, physical examinations, 12-lead ECGs, vital signs (including temperature, respiratory rate, and seated blood pressure and pulse), clinical chemistry laboratory evaluations, additional laboratory evaluations including prothrombin time/international normalized ratio (PT/INR), activated partial thromboplastin time (aPTT), hematology panel, urinalysis, and pregnancy test (female patients of child bearing potential only).

Statistical Methods:

Demographic and other patient data will be summarized by treatment group using descriptive statistics.

The primary efficacy comparison will compare the SelK2 only-treated, SelK2 and enoxaparin-treated, and enoxaparin only-treated arms. The difference in the total VTE rate determined during the entire Treatment Phase will be estimated. The 1-sided lower 90% CI of the difference between the SelK2 and enoxaparin groups only arms as well as the difference between the adaptive arm (SelK2 and enoxaparin) and enoxaparin only arms will be calculated and non-inferiority will be concluded if the upper limit of the 90% CI is $\leq 15\%$. Absolute changes from baseline in levels of high-sensitivity CRP and D-dimer will be assessed. A number of secondary analyses may be conducted to assess the robustness of the primary analysis finding.

SelK2 concentrations will be summarized by descriptive statistics.

Safety will be assessed by reported adverse events, changes from baseline during treatment in vital signs, ECGs, laboratory parameters, and physical examination and will be summarized using descriptive statistics. Adverse events will be coded using the (Medical Dictionary for Regulatory Activities) MedDRA dictionary and summarized by system organ class, preferred term, Investigator causality assessment, and treatment group. Incidence of bleeding events (as adjudicated by CIAC) will be tabulated by treatment group.

Sample Size Considerations:

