1.0 INTRODUCTION

1.1 Background

Deep vein thrombosis and pulmonary embolism are collectively referred to as venous thromboembolism (VTE). Venous thromboembolism is a major medical burden affecting millions of people around the world, with approximately 300,000 deaths and 540,000 deaths annually in the United States and the European Union, respectively. Current therapies available for venous thromboembolism include low-molecular-weight heparins (e.g., enoxaparin sodium), vitamin K antagonists (e.g., warfarin), and newer oral anticoagulants (e.g., rivaroxaban; a factor Xa inhibitor). These therapies target the coagulation system and can therefore result in the feared complication of hemorrhage, which can sometimes be fatal.

VTE is one of the most serious complications experienced by patients undergoing joint replacement surgeries such as total knee arthroplasty (TKA). Following elective TKA, objective venographic evidence of primarily asymptomatic deep vein thrombosis (DVT) occurs in 41-85% of patients without thromboprophylaxis. Because of the strong concordance between asymptomatic DVT detected by venography and clinically important VTE, DVT detected by contrast venography is most often used in the early investigation of new antithrombotic agents (1).

Considering the high incidence of VTE following TKA, the use of routine thromboprophylaxis is recommended in these patients. However, agents available for use in this patient population block the coagulation system and can cause major bleeding events leading to significant morbidity and mortality. There is a continuing medical need for the development of novel antithrombotic agents, especially those that may operate through a unique mechanism of action which is not associated with an increase in bleeding risk.

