1.4 Study Rationale

Venous thromboembolism is a major medical burden affecting millions of people around the world, with approximately one million cases and 300,000 deaths annually in the United States and approximately 1.5 million cases and 540,000 deaths annually in the European Union.

Approved therapies and standard of care available for use in VTE target the coagulation system and can therefore result in major bleeding events leading to significant morbidity and mortality. There is a continuing medical need for the development of novel antithrombotic agents, especially those that may operate through a unique mechanism of action which are not associated with an increase in bleeding risk.

This randomized, active comparator-controlled, open-label study is being conducted to determine the efficacy and safety of SelK2 when administered once to patients undergoing primary unilateral total knee arthroplasty. The study will compare the efficacy and safety of SelK2 to the standard of care, enoxaparin. The primary endpoint to assess clinical efficacy will be the composite of asymptomatic DVT, detected by mandatory unilateral venography, and objectively confirmed symptomatic VTE during the treatment phase of the study. The primary safety outcome is a combination of major bleeding events and clinically relevant non-major bleeding events during the treatment phase.

This study includes an adaptive arm that investigates the efficacy and safety of SelK2 use in combination with enoxaparin. This adaptive arm may be initiated if the Steering and Safety Committee determines that preliminary data suggests the potential of an additive effect in VTE reduction and that the combination does not pose an additional safety risk. The data obtained from this Phase 2 study will be used to provide evidence to support the claim of efficacy and safety of SelK2 in this patient population.

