10.3 Statistical Analysis

10.3.1 General Considerations

Descriptive summary statistics include mean, median, standard deviation, interquartile range, and range (minimum, maximum) for continuous variables, and counts and percentages for categorical

variables. Unless otherwise specified, continuous variables will be analyzed using two-sample t-test or Wilcoxon-Mann-Whitney test, whichever is appropriate; and categorical variables will be analyzed using chi-squared test or Fisher's exact test, whichever is appropriate.

SAS 9.3 or later will be used to perform statistical analysis. Unless otherwise specified, a two-sided p-value less than 0.05 will be considered statistically significant. No multiplicity adjustment will be made.

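### The primary safety outcome, major or clinically relevant non-major bleeding, is only tabulated by arm: no between-arm difference or interval is planned, although the protocol says safety will be compared with enoxaparin

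*Combined protocol and SAP*

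**What the plan says.** The Protocol Synopsis, under Safety, defines the outcome: "The primary safety outcome is a composite of major bleeding events or clinically relevant non-major bleeding events during the Treatment Phase". Section 2.0 lists assessment of bleeding incidence among the primary objectives. Section 1.4 states a comparative aim: "The study will compare the efficacy and safety of SelK2 to the standard of care, enoxaparin".

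The planned analysis is a tabulation. The Synopsis, under Statistical Methods, says: "Incidence of bleeding events (as adjudicated by CIAC) will be tabulated by treatment group". Section 10.4 says: "Incidence of bleeding events (as adjudicated by the CIAC) including the following will be tabulated by treatment", and lists major, clinically relevant non-major and minor bleeding, and the combination of the first two. It sets the period for safety analysis as "from randomization through the final Follow-Up Phase visit (Day 57") and closes with: "Descriptive analysis of the above safety parameters will be performed".

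Section 10.3.1 gives a general default for cases where nothing else is specified: "categorical variables will be analyzed using chi-squared test or" Fisher's exact test.

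The other endpoints get more. In 10.3.3 the VTE rate has an estimated difference, a confidence limit and a 15-point margin, and hsCRP and D-dimer have a between-group repeated-measures model. In 10.5 the interim tables give VTE rates and their difference with 80% intervals. Bleeding in those tables is tabulated only.

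**The concern.** Bleeding is central to the case for the drug. Section 1.1 describes a need for "novel antithrombotic agents, especially those that may operate through a unique mechanism of action which is not associated with an increase in bleeding risk", and the VTE comparison tolerates an excess of up to 15 points. A reader weighing that tolerance will look to the bleeding comparison. As planned, that reader gets a percentage per arm with no measure of how far apart the true rates could be.

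Two decisions are exposed. At the end of the trial, similar percentages could be taken as no more bleeding, and a small favourable gap as less bleeding, when the data fit either. During the trial, 10.5 lets the committee recommend the combination arm only if it judges that the combination adds no safety risk, and the bleeding table listed there carries no interval.

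A second gap sits in the same section. The outcome is defined for the Treatment Phase, but 10.4 runs the safety analysis to Day 57 and states no separate Treatment Phase tabulation.

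**Working it through.** **The plan's own figure.** Section 10.1 uses 25% VTE in both arms, a 15-point margin, one-sided 0.10 and 80% power:

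n = (1.2816 + 0.8416)² × (2 × 0.25 × 0.75) / 0.15² = 4.508 × 0.375 / 0.0225 = 75.1, so 76 evaluable per arm; 76 / 0.80 = 95 enrolled.

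This reproduces, but it concerns VTE only. The documents contain no rate, margin or power for bleeding.

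**Precision for bleeding.** The safety population (10.2) is all dosed patients, so at most about 95 per arm. The counts below are assumptions. With p = x/n and z = 1.96, the Wilson limits (l, u) for one arm are

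[p + z²/(2n) ± z√(p(1−p)/n + z²/(4n²))] / (1 + z²/n).

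The Newcombe limits for d = p₁ − p₂ (SelK2 minus enoxaparin) are

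lower = d − √((p₁−l₁)² + (u₂−p₂)²), upper = d + √((u₁−p₁)² + (p₂−l₂)²).

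- *3/95 versus 3/95.* Each arm is 3.16% (Wilson 1.08 to 8.88). Half-width = √(2.08² + 5.72²) = 6.1 points.
- *1/95 versus 4/95.* The arms are 1.05% (0.19 to 5.72) and 4.21% (1.65 to 10.33), so d = −3.16. Lower = −3.16 − √(0.87² + 6.12²) = −9.3. Upper = −3.16 + √(4.67² + 2.56²) = +2.2.

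| SelK2 vs enoxaparin | Difference (points) | Newcombe 95% CI |
|---|---|---|
| 3/95 vs 3/95 | 0.0 | −6.1 to +6.1 |
| 5/95 vs 5/95 | 0.0 | −7.1 to +7.1 |
| 10/95 vs 10/95 | 0.0 | −9.1 to +9.1 |
| 1/95 vs 4/95 | −3.2 | −9.3 to +2.2 |
| 2/95 vs 6/95 | −4.2 | −11.2 to +2.0 |
| 2/48 vs 2/48 | 0.0 | −10.3 to +10.3 |

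**Why 48.** If the combination arm opens, the SelK2-only arm closes. Section 5.1.3 sets a 2:1 ratio so that the two remaining arms end about equal. With 95 in each at the end and k enoxaparin patients already enrolled, 95 = 2 × (95 − k), so k = 47.5. Under 1:1 allocation the SelK2-only arm would then stop at about 48. The last row compares it with the 48 enoxaparin patients randomized alongside it. The same arithmetic puts about 48 of the 95 enoxaparin patients before the switch and about 47 after, so the choice of controls for the combination arm matters.

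**What a default test would add.** Fisher's exact test on 3 versus 3 returns p = 1, whereas the interval still allows an excess of 6 points. A p-value does not supply the missing quantity.

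**Why this cannot be a powered test.** For two-sided 5% and 80% power, with p̄ the mean of the two rates, n = [1.96√(2p̄(1−p̄)) + 0.8416√(p₁(1−p₁) + p₂(1−p₂))]² / (p₁−p₂)². Assumed rates of 1% versus 5% need (0.4729 + 0.2016)² / 0.0016 = 284.3, so 285 per arm. Rates of 5% versus 10% need (0.7301 + 0.3121)² / 0.0025 = 434.4, so 435 per arm.

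**The case against.** Descriptive safety analysis is usual in a phase 2 trial sized for efficacy, and much of what protects this outcome is in place. The composite is defined, adjudication is blinded, the safety population is analysed as treated, and the composite has its own row in the table. Anyone with counts and denominators can compute an interval. The committee does see adjudicated bleeding by arm, and its charter, which is not available here, may specify more. The wide intervals above partly restate that 95 per arm is few.

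Most of that stands, and it keeps the point modest. It does not explain why the one named primary safety outcome, with a stated comparative aim, gets no planned contrast. In an open-label trial, an interval chosen after the results are known is worth less than one fixed beforehand.

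Three stronger readings are tempting, and the documents do not support them:

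- *That the plan formally claims less bleeding than enoxaparin.* Sections 1.1 to 1.2 give a medical need and primate data, and section 2.0 only assesses incidence. There is no bleeding hypothesis, margin or decision rule.
- *That 10.4 overrides the default test in 10.3.1.* The closing sentence of 10.4 follows two lists, bleeding first and then, introduced separately, adverse events, laboratory values, ECGs and vital signs. It may cover both or mainly the second. A test of bleeding may therefore already be intended.
- *That the trial should be enlarged for bleeding.* Nothing in the documents makes bleeding a powered comparison.

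**Conclusion.** The point holds as a low-cost improvement. The protocol says it will compare safety with enoxaparin, but the planned output for the primary safety outcome contains no between-arm estimate or interval. The default test in 10.3.1, if it applies, would not provide one. The plan also leaves open whether the Treatment Phase outcome will be analysed over its own window.

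The size depends on bleeding rates that the documents do not give. For equal counts of 3 to 10 per arm, the 95% interval is about ±6 to ±9 points at 95 per arm, and about ±10 for 2 versus 2 if the SelK2-only arm closes near 48. A fourfold gap of 1 versus 4 still includes zero. These figures assume that nearly all enrolled patients are dosed.

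**What to change.** In 10.4, for the safety population:

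1. Report the proportion of patients with adjudicated major or clinically relevant non-major bleeding in the Treatment Phase, and the risk difference with a two-sided 95% score-type interval (name one: Newcombe or Miettinen-Nurminen). Do this for SelK2-only minus enoxaparin and, if that arm opens, for SelK2 plus enoxaparin minus enoxaparin.
2. Report the same contrast through Day 57 as a secondary analysis.
3. State which enoxaparin patients, those randomized before the 2:1 switch, after it, or both, are the controls for the combination arm.
4. State that bleeding conclusions rest on the interval as estimation and not on a powered test, and say whether the 10.3.1 default test applies to bleeding.
5. Show the same interval in the 10.5 committee tables.

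No patients or data are added. The cost is some programming, a decision on window and controls, and an interval wide enough to limit what can be said about bleeding.
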